8.7 Pharmacokinetic Analysis Set

The PK analysis set consists of all subjects who received at least 1 full or partial dose of OP-1250 and have adequate PK samples for PK parameter characterization.

9. STUDY SUBJECTS AND DEMOGRAPHICS

9.1 Subject Disposition

Subject disposition summary will include: the number of subjects in each analysis set, the number of subjects discontinued the study treatment, the primary reason for study treatment discontinuation, the number of subjects completed the study, the number of subjects discontinued the study early, and the primary reason for study discontinuation.

9.2 Protocol Deviations

Important protocol deviations (IPD) are a subset of protocol deviations that may significantly impact the completeness, accuracy, and/or reliability of the study data or that may significantly affect a subject's rights, safety, or well-being and will be identified before database lock. Important protocol deviations may include, but are not limited to:

- Enrolled subjects who did not satisfy selected inclusion and exclusion criteria.
- Enrolled subjects who developed withdrawal criteria during the study but were not withdrawn.
- Subjects who received the incorrect dose.
- Subjects who received a prohibited medication.

Important protocol deviations will be summarized by deviation category.

9.3 Demographic and Baseline Characteristics

Demographic and baseline characteristics and cancer history will be summarized for the safety analysis set.

Demographic variables include age, age group, sex, ethnicity, and race. Age will be calculated in years relative to the informed consent date.

Other baseline characteristics include height, weight, body mass index (BMI), Eastern Cooperative Oncology Group Performance Status (ECOG PS), menopausal status (for females) [REDACTED]

The summary of cancer history will include but not limited to the following characteristics:

- Time from initial metastatic or recurrent BC diagnosis to first dose date
- Brain metastases at initial metastatic or recurrent BC diagnosis (yes/no)
- Overall grade at time of initial metastatic or recurrent BC diagnosis
- Histology at time of initial metastatic or recurrent BC diagnosis
- Estrogen receptor status at time of initial metastatic or recurrent BC diagnosis
- Progesterone receptor status at time of initial metastatic or recurrent BC diagnosis
- HER2 status at time of initial metastatic or recurrent BC diagnosis
- Surgery for metastatic or recurrent BC (yes/no, type)
- Radiotherapy for metastatic or recurrent BC (yes/no)
- Sites of disease at study entry

- Overall grade at study entry
- Estrogen receptor status at study entry
- Progesterone receptor status at study entry
- HER2 status at study entry
- Visceral disease

The prior systemic treatment for metastatic or recurrent breast cancer will include the followings:

- Number of systemic treatment regimens for metastatic or recurrent BC
- Number of systemic hormonal treatment regimens for metastatic or recurrent BC
- Types of therapies

9.4 Medical history

The verbatim term of the medical history condition/event will be coded using Medical Dictionary for Regulatory Activities (MedDRA). A summary will be presented by system organ class (SOC) and preferred term (PT).

9.5 Prior and Concomitant Medications

Prior and concomitant medication will be summarized for the safety analysis set.

Prior and concomitant medication verbatim terms in the eCRFs will be mapped to Anatomical/Therapeutic/Chemical (ATC) class and Preferred Names using World Health Organization (WHO) Drug Global Dictionary WHODDE B3 March 1, 2020.

Concomitant medications are those started after the initial dose of OP-1250 through last dose + 30 days or medications started prior to initial dose of OP-1250 and continued during the treatment period. Prior medications are those that started prior to initial dose of study drug. Note that medications can be classified as both prior and concomitant.

Concomitant medications will be summarized by WHO ATC class and preferred name. This summary will present the numbers and percentages of subjects using each medication. Subjects may have more than 1 medications per ATC class and preferred name. At each level of subject summarization, a subject is counted once if he/she reported 1 or more medications at that level.

10. EFFICACY ANALYSES

Efficacy analyses for ORR [REDACTED] by investigator assessment will be conducted using EFS with measurable disease at baseline (without cohort C). CBR by investigator assessment will be summarized using CBR analysis set. [REDACTED]

[REDACTED]

[REDACTED]

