## 8 INVESTIGATIONAL PLAN

### 8.1 Overall Study Design and Plan

This is a Phase I dose escalation and dose expansion and Phase II monotherapy open-label, first-in-human study to determine the dose limiting toxicity (DLT), maximum tolerated dose (MTD) and/or recommended Phase II dose (RP2D), to characterize the safety and pharmacokinetic (PK) profile, and to estimate the preliminary antitumor activity of OP-1250 as a single agent in adult subjects with hormone receptor (HR)-positive/human epidermal growth factor receptor 2 (HER2)-negative metastatic or locally advanced breast cancer. Treatment and study subject evaluation will be performed in 28-day cycles. This study comprises 2 Phases: Phase I (Part A [Dose Escalation] and Part B [Dose Expansion]) and Phase II.

**Phase I: Part A (Dose Escalation) and Part B (Dose Expansion):** This portion of the study will evaluate the safety and PK of a range of doses of OP-1250 administered orally to subjects and determine the MTD and/or RP2D. Part A will employ a rolling 6 dose escalation study design, whereby cohorts of 3 to 6 subjects will be sequentially enrolled and monitored for DLTs during the first cycle of study treatment. Part B will enroll approximately 30 subjects in the expansion phase at the RP2D, or in the event 2 dose levels are being considered for the RP2D, then approximately 30 subjects will be enrolled in each of the 2 dose levels. Approximately 42 subjects will be enrolled in Part A (dose escalation), and up to approximately 60 subjects will be enrolled in Part B (dose expansion). Up to a total of approximately 102 subjects may be enrolled in the Phase I portion of the study.

**Phase II:** This portion of the study further explores the clinical activity, safety, and PK of OP-1250 at the RP2D and will estimate the preliminary anti-tumor efficacy. Up to 88 evaluable subjects will be enrolled over 3 cohorts in the Phase II: Cohort A will enroll 50 subjects with measurable disease without evidence of CNS metastases (subjects in the expansion at the RP2D will be included in this cohort), Cohort B will enroll approximately 15 subjects with non-measurable (evaluable) disease without evidence of CNS metastases; and Cohort C will enroll approximately 15 subjects with CNS metastases. To allow for subject replacement up to a total of approximately 88 subjects may be enrolled in the Phase II portion of the study.

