***Additionally, for individuals eligible to participate in Part A (Dose Escalation) of the Phase I portion of the study:***

- 21. The subject must have received no more than 2 prior chemotherapy regimens for locally advanced or metastatic disease.
- 22. Subjects must have evaluable disease. Subjects with both measurable and non-measurable disease are eligible.

***Additionally, for individuals eligible to participate in Part B (Dose Expansion) of the Phase I portion of the study and in the Phase II portion:***

- 23. Subjects must have measurable disease by RECIST 1.1 criteria
- 24. The subject must have received no more than 1 prior chemotherapy regimen for locally advanced or metastatic disease.
- 25. The subject must have had at least 1 and no more than 4 prior hormonal-based therapies for locally advanced, recurrent, or metastatic disease.
- 26. Subjects with brain metastases are eligible for the study (Phase I Part A, Phase I Part B, and Phase II Cohort C) if they meet all the following criteria:
  - a. The subject's brain metastases have been treated or do not require urgent local treatment at the time of study enrollment.
  - b. The subject has been off dexamethasone or is on a stable dose of dexamethasone of  $\leq 2$  mg daily (or an alternate steroid dosed at a level equal to  $\leq 2$  mg daily) for at least 2 weeks prior to first study drug administration.

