3. STUDY ENDPOINTS

The study endpoints of each of the 2 phases of the study are:

Phase I (Dose Escalation and Expansion)

Primary Endpoints:

- Incidence and nature of DLTs as defined in the protocol.
- MTD and/or RP2D of OP-1250 when used as a single agent.
- Incidence, nature, and severity of treatment-emergent Adverse Events (TEAEs) and serious adverse events (SAEs) according to NCI-CTCAE version 5.0.
- Plasma levels of OP-1250 at pre-defined intervals to establish PK parameters (includes maximum concentration (C_{max}), minimum concentration (C_{min}), time to maximum concentration (T_{max}), area under the curve (AUC), half-life (t_{1/2}), and OP-1250 trough concentration at steady state).

Secondary Endpoints:

- ORR by evaluation of tumor response assessments using RECIST 1.1 in subjects with measurable disease.
- CBR as defined by percent of subjects with CR + PR + SD \geq 24 weeks, by evaluation of tumor response assessments using RECIST 1.1.

• [REDACTED]

[REDACTED]

- [REDACTED]
- [REDACTED]
- [REDACTED]
- [REDACTED]
- [REDACTED]
- [REDACTED]

Phase II

Primary Endpoints:

- ORR by evaluation of tumor response assessments using RECIST 1.1 in subjects without evidence of CNS metastases who have measurable disease.
- Incidence, nature, and severity of TEAEs and SAEs according to National Cancer Institute-Common Terminology Criteria for Adverse Events (NCI-CTCAE) version 5.0.
- Plasma levels of OP-1250 at pre-defined intervals to establish PK parameters (includes C_{max}, C_{min}, T_{max}, AUC, t_{1/2}, and OP-1250 trough concentration at steady state). The results of those analyses will be reported separately in PK report.

Secondary Endpoints:

- CBR as defined by percent of subjects with a CR + PR + SD for ≥ 24 weeks, by evaluation of tumor response assessments using RECIST 1.1 in subjects without evidence of CNS metastases.

█

████████████████████

█

█

█

█

█

█

█

█

█

█

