5.3 Phase II

Approximately a total of 80 additional subjects will be enrolled in the expansion phase: 50 subjects in Cohort A, 15 in Cohort B, and 15 in Cohort C. Subjects not evaluable may be replaced.

For the statistical analyses of ORR, data from the 50 subjects in Cohort A who were dosed at the RP2D will be included. A sample size of 50 subjects will provide an estimation precision of $\pm 15\%$ for any binary event assessing safety (e.g., any SAE's) or anti-tumor activity (e.g., overall response, clinical benefit). This level of precision is regarded as clinically sufficient in the preliminary estimation of the risk:benefit profile to plan future clinical trials for OP-1250's clinical development plan.

Subjects without measurable disease are being enrolled in the Phase II study (Cohort B) in order to mimic the general population of ER+ breast cancer subjects, many of which have bone only disease. Subjects without measurable disease in the Phase II are limited to a total of 15 subjects and will not be included in the determination of ORR; however, they will be included in safety, secondary, and exploratory analyses where appropriate [REDACTED]

[REDACTED]

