6. GENERAL ANALYSIS CONSIDERATIONS

6.1 Statistical Analysis Cohorts

Statistical analysis will be conducted in the cohorts below.

1. Dose Escalation subjects: All endpoints [REDACTED] will be summarized by dose groups.
2. Subjects treated at 60 mg or 120 mg pooled from dose escalation, dose expansion and phase II (without cohort C): The study subjects and demographic, pharmacodynamic endpoints, and efficacy endpoints will be analyzed by dose groups.

- [REDACTED]
4. All subjects: All safety related endpoints will be summarized based on the safety analysis set by dose groups, [REDACTED] and overall.

For summary by dose groups, the dose groups will be based on the first doses the subjects received.

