8.5 Efficacy Analysis Set

The efficacy analysis set (EFS) will include all subjects who received at least 1 cycle of OP-1250 and have at least 1 post-baseline tumor assessment.

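### The SAP screens CNS metastases out of the Phase II primary ORR by cohort label rather than by CNS status, and the documents do not agree on which subjects make up the 50

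*SAP*

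**What the plan says.** **Endpoint.** SAP Section 3 gives the Phase II primary endpoint as "ORR by evaluation of tumor response assessments using RECIST 1.1 in subjects without evidence of CNS metastases who have measurable disease". Protocol Table 5 agrees. The protocol synopsis (Efficacy Analyses) adds that subjects with CNS metastases are analysed separately.

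**Who may have brain metastases.** Protocol Section 8.3.1, criterion 26: "Subjects with brain metastases are eligible for the study (Phase I Part A, Phase I Part B, and Phase II Cohort C"). Criterion 28 bars CNS metastases from Cohort A.

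**ORR rule.** SAP Section 10 says the ORR analyses "will be conducted using EFS with measurable disease at baseline (without cohort C"). The EFS (SAP Section 8.5) "will include all subjects who received at least 1 cycle of OP-1250" and have a post-baseline tumor assessment. It has no restriction on phase, dose or CNS status. The confirmed-ORR definition in SAP Section 10.1 uses the EFS with measurable disease and names no cohort.

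**Efficacy pool.** SAP Section 6.1, item 2: "Subjects treated at 60 mg or 120 mg pooled from dose escalation, dose expansion and phase II (without cohort C"), analysed by dose group.

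**The 50.** Protocol Section 8.1 (likewise the synopsis subject numbers and Section 8.6) sets Cohort A at 50 and states that "subjects in the expansion at the RP2D will be included in this cohort". An earlier synopsis paragraph says only that they may be. Protocol Section 11.4.3 says Part B subjects at the RP2D contribute to the activity estimate and then refers to all 50. SAP Section 5.3 says: "Approximately a total of 80 additional subjects will be enrolled in the expansion phase: 50 subjects in Cohort A", and bases ORR on the 50 Cohort A subjects dosed at the RP2D.

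**The concern.** The endpoint is defined by a patient characteristic, while the analysis rule is defined by an enrolment label. The two coincide only if Cohort C is the sole place where subjects with CNS metastases can be found, and criterion 26 says it is not. The primary estimate could therefore describe a population other than the one the endpoint names.

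The second difficulty is reproducibility. Two programmers working from these documents could produce different primary ORRs, one on 50 subjects and one on about 80, each with text to support the choice. The trial is open-label, Protocol Section 11.4.2 plans a review of Part B anti-tumor activity before Phase II, and SAP Section 6.2 claims pre-specification only relative to database lock. The denominator should not be left to be settled once responses are known.

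**Working it through.** **1. The plan's own precision figures.** SAP Section 10.2 specifies Clopper-Pearson intervals. For x responders of n, the lower limit is the 2.5% quantile of Beta(x, n − x + 1) and the upper limit is the 97.5% quantile of Beta(x + 1, n − x). The half-width is (upper − lower)/2, taken at its largest over all x.

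- n = 50: 14.5 points; largest distance from estimate to limit 14.8. Stated: ±15%. Reproduced.
- n = 30: 18.7 points; largest distance 19.5. Stated: ±19%. Reproduced.

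The smallest n with a worst-case half-width of at most 15 points is 47; for the estimate-to-limit distance it is 49.

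**2. Which n applies at 120 mg.** Part B plans 30 subjects at 120 mg (Protocol Section 8.8.4). The Part A number at 120 mg is not given. I assume 3 to 6, from the planned cohort size, all with measurable disease and evaluable.

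| Reading | Source | n | Worst-case half-width |
|---|---|---|---|
| 50 includes about 30 from Part B (50 − 30 = about 20 new) | Protocol 8.1, 11.4.3 | 50 | 14.5 |
| 50 newly enrolled in Cohort A, Part B not pooled | SAP 5.3 | 50 | 14.5 |
| 50 newly enrolled plus 30 from Part B | SAP 5.3 with SAP 6.1 | 80 | 11.4 |
| As above plus 3 to 6 from Part A | SAP 5.3 with SAP 6.1 | 83 to 86 | 11.2 to 11.0 |

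The first two readings share an n but not the same people. At an assumed ORR of 20%, 10/50 gives a 95% CI of 10.0% to 33.7%, and 16/80 gives 11.9% to 30.4%.

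**3. Tracing a Part B subject with brain metastases.** Take a subject at 120 mg with measurable disease who meets criterion 26.

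- SAP 8.5: in the EFS after one cycle and one post-baseline scan.
- SAP 6.1, item 2: in the 120 mg pool, because the subject is not in Cohort C.
- SAP 10: in the ORR analysis, for the same reason.
- Protocol 8.1: counted into Cohort A as an expansion subject at the RP2D, with no CNS condition attached to that step.
- Phase II primary endpoint: should be out.

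No visible step in the SAP's ORR rule removes the subject. The same holds for the Phase II CBR. Its endpoint also excludes CNS metastases, while SAP 10.1 again drops only Cohort C.

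**4. Possible size.** The number k of such subjects is not in the documents. Suppose all k are non-responders and the apparent ORR is 20%. The ORR without them is 16/(80 − k) or 10/(50 − k):

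| k (assumed) | Set of 80 | Set of 50 |
|---|---|---|
| 1 | 20.3% | 20.4% |
| 3 | 20.8% | 21.3% |
| 6 | 21.6% | 22.7% |
| 9 | 22.5% | 24.4% |

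For k of 1 to 3 the shift is 0.3 to 1.3 points. At 20% the interval half-width is (30.4 − 11.9)/2 = about 9.3 points for n = 80 and (33.7 − 10.0)/2 = about 11.8 points for n = 50.

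**The case against.** The best defence is that the intended primary set can be recovered. SAP Section 5.3 bases ORR on Cohort A, where criterion 28 bars CNS metastases. SAP Section 10.1 calls ORR primary in Phase II and only secondary in Phase I. The protocol synopsis keeps CNS subjects separate. Protocol Section 8.1 describes Cohort A as free of CNS metastases in the same sentence that brings in the expansion subjects, so the condition may be meant to carry over. The pool in SAP Section 6.1 is a summary by dose group and is not labelled primary. Item 3 of that section and parts of SAP Sections 5.3 and 10 are redacted and could hold a further rule. Finally, this is single-arm estimation with no hypothesis test and no formal interim analysis.

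Much of this stands. It means that Phase I subjects with CNS metastases *could* enter the primary ORR, not that they necessarily do. It also means the ambiguity bears on what is estimated and reported, not on type I error. It does not remove the defect. Part B subjects were admitted under criterion 26 rather than criterion 28, and the text that moves them into Cohort A does not restate the CNS condition. The visible ORR rule in SAP Section 10 is looser than the endpoint it serves. Nor does the defence reconcile the two meanings of the 50.

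**Conclusion.** The concern holds in this form: the visible ORR rule does not match the Phase II primary endpoint, and the documents give more than one ORR set. The 120 mg denominator is 50 or about 80, or about 83 to 86 under the Part A assumption. The effect of any CNS subjects on the estimate is probably small, but it depends on a count the documents do not give.

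Three stronger conclusions might be inferred and are not supported:

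- *That subjects with brain metastases are certain to be in the primary ORR.* SAP Section 5.3 and criterion 28 point the other way, and relevant text is redacted.
- *That the stated precision is wrong or lost.* ±15% is correct for n = 50, and every candidate denominator from 50 to 86 meets it. The roughly 20 new subjects implied by the protocol's reading would give 22.8 points alone, but no passage proposes analysing them alone.
- *That CNS subjects should leave every ORR analysis.* The Phase I secondary ORR covers subjects with measurable disease and has no CNS exclusion.

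**What to change.** 1. In SAP Sections 10 and 10.1, define the Phase II primary ORR set once: EFS, measurable disease at baseline, no evidence of CNS metastases at baseline (by status, not cohort label), first dose at the RP2D, and named study parts. Part B at the RP2D plus Cohort A would follow Protocol Section 11.4.3.
2. Apply the same CNS-status filter to the Phase II CBR. Leave the Phase I secondary ORR and the demographic and pharmacodynamic summaries in SAP Section 6.1 as they are.
3. Delete the word *additional* from SAP Section 5.3, or keep it and restate n and precision for the pooled set (about 80, worst-case half-width 11.4 points). Align the protocol's *will be included* and *may be included* wording with that choice.
4. As a minor alignment, the protocol gives up to 88 evaluable in the synopsis and Sections 8.1 and 8.6, but 80 in Section 8.9. The cohorts sum to 50 + 15 + 15 = 80, and 88 is the replacement allowance. Reporting ORR by study part is optional.

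The cost is SAP wording and a short protocol clarification, with no new data collection. A few subjects may leave the primary set. About 47 to 49 evaluable subjects are enough to keep ±15%.

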10.1 Efficacy Endpoints

ORR

ORR is the primary efficacy endpoint in phase II (without cohort C) and secondary endpoint in phase I. Objective response will be determined using RECIST version 1.1. The overall tumor response at each time point will be recorded. A subject's best overall response will be derived as the best response over all time points, where responses from best to worst are CR, PR, SD, progressive disease (PD), and not evaluable (NE). Time point responses after the first assessment of PD will not be used in the derivation of confirmed best objective response. A confirmed response requires a CR or PR to be confirmed at a subsequent tumor assessment at least 4 weeks (28 days) from the initial assessment of CR or PR, and a confirmed response of SD requires the interval from first dose date to SD to be at least 6 weeks (42 days). To determine the best overall confirmed response in the presence of at least one time point response of CR or PR, the best response for each pair of assessments will be derived based on Table 2. The best overall confirmed response will then be the best over all of the pair best responses.

Table 2: Derivation of Best Overall Response when confirmation of CR and PR required

Overall response for 1 st time point	Overall response for subsequent time point	Best overall response for pair of assessments
CR	CR	CR if time requirement is met, otherwise NE
CR	PR	SD or PD or PR ^a
CR	SD	SD provided minimum criteria for SD duration met, otherwise, PD
CR	PD	SD provided minimum criteria for SD duration met, otherwise, PD
CR	NE	SD provided minimum criteria for SD duration met, otherwise NE
PR	CR	PR

PR	PR	PR
PR	SD	SD
PR	PD	SD provided minimum criteria for SD duration met, otherwise, PD
PR	NE	SD provided minimum criteria for SD duration met, otherwise, NE
NE	NE	NE

CR=complete response; PR=partial response; SD=stable disease; PD=progressive disease; NE=not evaluable.

^a : If a CR is truly met at first time point, then any disease seen at a subsequent time point, even disease meeting PR criteria relative to baseline, makes the disease PD at that point (since disease must have reappeared after CR). Best response would depend on whether minimum duration for SD was met. However, sometimes 'CR' may be claimed when subsequent scans suggest small lesions were likely still present and in fact the patient had PR, not CR at the first time point. Under these circumstances, the original CR should be changed to PR and the best response is PR.

The confirmed ORR is defined as the proportion of subjects with a best overall response of confirmed CR or PR in EFS with measurable disease at baseline.

The secondary efficacy endpoints for Phase II are:

CBR

CBR is defined as the proportion of subjects with a confirmed CR, PR, or SD and who had been on treatment for ≥ 24 weeks. Subjects who had disease progression per RECIST 1.1 7 days before Cycle 7 day 1 will not be considered as clinical benefit. Duration of treatment is defined as time from the first dose date of study treatment to end of treatment date for subjects discontinued treatment or to data cutoff date for ongoing subjects.

CBR will be summarized based on CBR Analysis Set (without cohort C) defined in 8.6.

[REDACTED]

[REDACTED]

[REDACTED]

[REDACTED]	[REDACTED]	[REDACTED]
------------	------------	------------

[REDACTED]	[REDACTED]	[REDACTED]
[REDACTED]	[REDACTED]	[REDACTED]
[REDACTED]	[REDACTED]	[REDACTED]
[REDACTED]	[REDACTED]	[REDACTED]

[REDACTED]

[REDACTED]

[REDACTED]

[REDACTED]

[REDACTED]	[REDACTED]	[REDACTED]
[REDACTED]	[REDACTED]	[REDACTED]
[REDACTED]	[REDACTED]	[REDACTED]
[REDACTED]	[REDACTED]	[REDACTED]

[REDACTED]	[REDACTED]	[REDACTED]
[REDACTED]	[REDACTED]	[REDACTED]
[REDACTED]	[REDACTED]	[REDACTED]

[REDACTED]

[REDACTED]

[REDACTED]

[REDACTED]

[REDACTED]	[REDACTED]	[REDACTED]
[REDACTED]	[REDACTED]	[REDACTED]
[REDACTED]	[REDACTED]	[REDACTED]
[REDACTED]	[REDACTED]	[REDACTED]
[REDACTED]	[REDACTED]	[REDACTED]
[REDACTED]	[REDACTED]	[REDACTED]

[REDACTED]	[REDACTED]	[REDACTED]
------------	------------	------------

[REDACTED]

[REDACTED]

[REDACTED]

[REDACTED]

[REDACTED]

[REDACTED]

[REDACTED]

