9 Fasting lipid panel includes total cholesterol, high-density lipoprotein cholesterol, low-density lipoprotein cholesterol, and triglycerides.

10 Macroscopic assessment of the amount of protein, glucose, white blood cells, and blood (levels should be recorded if available) and microscopic analysis if abnormality is noted.

11 See PK sampling schedule in Table 2 for all subjects, [REDACTED]

14 Baseline CT (with contrast) or MRI of chest, abdomen, and pelvis must be obtained within 4 weeks prior to the first IP dose. The same method (CT with contrast or MRI) must be used throughout the study. Subjects with brain metastasis should have MRI scans of the brain.

16 Safety follow-up is to occur at 30 to 42 days after EOT visit. All related AEs will be followed to resolution, stabilization, or loss of contact with the subject. All unrelated AEs will be followed until the time of the Safety Follow-up visit, which is between 30 to 42 days after the EOT visit.

17 Radiographic assessment (and physical assessments of malignancy) should be performed at every 2 cycles starting at C3 (ie, C5, C7, C9, etc). Assessments must be performed prior to commencing treatment for that cycle. Post C9 assessment, for subjects who have been determined to have obtained a clinical benefit from OP-1250 may reduce frequency of assessments to every 3 cycles (ie, C12, C15, C18, etc.) prior to commencing treatment for that cycle.

18 Tumor assessments are to be performed on subjects who have not previously shown radiologic progression.

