### 8.11 Treatment Duration

In the absence of unacceptable OP-1250 treatment-related toxicity or disease progression, subjects may receive OP-1250 treatment for up to 1 year and beyond 1 year with the agreement of the investigator or designee and the sponsor.

Treatment will continue until any 1 of the following occurs:

- SAE or AE that requires dose discontinuation as described in [Section 8.10, Table 8](#).
- Progressive disease as determined by RECIST 1.1 (see [Appendix E](#)) (Tumor marker elevations in the absence of unequivocal radiologic progression of target or non-target lesions is not considered disease progression. Per RECIST 1.1, disease progression requires an overall disease burden increase based on the change in non-measurable disease that is comparable in magnitude to the increase that would be required to declare PD for measurable disease: ie, an increase in tumor burden representing an additional 73% increase in 'volume,' which is equivalent to a 20% increase in diameter in a measurable lesion.)
- Initiation of non-protocol anticancer therapy.
- Illness or condition that may interfere with the subject's participation or require treatment discontinuation.
- Treating investigator or designee's determination that continuation of protocol therapy is not in the subject's best interests.
- Pregnancy.
- Noncompliance.
- Voluntary withdrawal of consent.
- Sponsor termination of the study.

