### 10.5.3 End of Treatment

The EOT visit should occur within 42 days after administration of the last dose of IP.

For any subject who has been withdrawn from the study (see [Section 8.3.3](#)), the tests and evaluations listed for the EOT visit should be performed, if possible. The assessments to be performed at the EOT visit are detailed in the Schedule of Events in [Table 1](#).

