## 22.5 APPENDIX E: RECIST V1.1

Disease response in target and non-target lesions will be assessed by the Investigator using RECIST v1.1 ([https://ctep.cancer.gov/protocolDevelopment/docs/recist\\_guideline.pdf](https://ctep.cancer.gov/protocolDevelopment/docs/recist_guideline.pdf)), according to the categories and criteria described in Table 14. The best overall response for each subject will be reported as the best response documented over the sequence of objective statuses recorded using the categories and criteria in Table 15.

When possible, the same qualified physician will interpret results to reduce variability.

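### SAP 10.1 cuts off the response derivation at first PD but not at the start of other anticancer therapy, so an end-of-treatment scan on the next therapy can confirm a response in the Phase II primary ORR

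*SAP*

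**What the plan says.** **Derivation.** SAP 10.1 states: "A subject's best overall response will be derived as the best response over all time points". Its only exclusion is this: "Time point responses after the first assessment of PD will not be used in the derivation of confirmed best objective response". Confirmation comes from a later assessment at least 28 days after the first CR or PR, with no condition that the subject is still taking OP-1250. SAP Table 2 returns PR for a PR followed by a PR. The endpoint then follows: "The confirmed ORR is defined as the proportion of subjects with a best overall response of confirmed CR or PR in EFS", restricted to measurable disease at baseline. Protocol Appendix E gives no cut-off either; best overall response there is "reported as the best response documented over the sequence of objective statuses recorded".

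**How treatment ends.** Protocol 8.11 lists this among the events that end treatment: "Initiation of non-protocol anticancer therapy". Protocol 10.5.3 then says: "The EOT visit should occur within 42 days after administration of the last dose of IP". Table 1, footnote 18, governs the tumour scan at that visit: "Tumor assessments are to be performed on subjects who have not previously shown radiologic progression". Protocol 8.13 bars other cancer therapy while study treatment lasts, and does not address the interval from last dose to EOT.

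**Two limiting provisions.** Protocol 10.3.2 waives a tumour assessment if one was completed in the preceding 4 weeks. The last line of Appendix E calls for a repeat assessment 4 weeks after any CR or PR.

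**The concern.** ORR is the Phase II primary efficacy endpoint, and the study sets out to describe OP-1250 as a single agent. A subject may stop for toxicity, by choice or through clinical deterioration, without RECIST progression. The PD cut-off does nothing for this subject, because the EOT scan is reserved for people who have not progressed. If a new regimen, or radiotherapy or surgery to a target lesion, comes before that scan, the scan no longer reflects OP-1250 alone. Read literally, SAP 10.1 still lets it supply the missing confirmation. At stake is whether a responder counted for OP-1250 was confirmed on OP-1250.

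**Working it through.** **1. The plan's own figure.** SAP 5.3 states a precision of ±15% for 50 subjects, and SAP 10.2 specifies Clopper-Pearson intervals. At the widest point, 25/50, the 95% interval is 35.5% to 64.5%. The half-width is (64.5 − 35.5)/2 = 14.5 points, which rounds to the stated figure.

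**2. Can an EOT scan meet the 28-day rule?** Let *g* be the days from the first CR/PR scan to the last dose. The EOT scan falls between *g* and *g* + 42 days after that first scan. Since *g* + 42 ≥ 28 for every *g* ≥ 0, the rule can always be met: *g* = 0 gives 0 to 42 days, *g* = 14 gives 14 to 56, and *g* = 28 gives 28 to 70.

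**3. How far the limiting provisions narrow this.** Suppose the 4-week repeat scan is always done on time. A subject with *g* ≥ 28 then has the repeat scan by the last dose, so exposure is confined to *g* < 28. For these subjects an EOT scan can confirm only if it falls from 28 − *g* to 42 days after the last dose:

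| *g* (days) | EOT scan that can confirm (days after last dose) |
|---|---|
| 0 | 28 to 42 |
| 10 | 18 to 42 |
| 14 | 14 to 42 |
| 27 | 1 to 42 |

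The skip rule waives most EOT scans earlier than this. By the same token, an EOT scan that is required will usually be about 28 days or more after the previous one.

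**4. Example (dates assumed).** The first PR is at C3D1, day 1 + 2 × 28 = 57. The last dose is on day 67, so *g* = 10. Another regimen starts on day 70. An EOT scan can confirm from day 57 + 28 = 85 to day 67 + 42 = 109, after 85 − 70 = 15 to 109 − 70 = 39 days of the new regimen. If it still shows PR, there is no PD to trigger the exclusion, Table 2 gives PR, and the subject is a confirmed responder. The Appendix E repeat would also fall due on day 85, already on the new regimen.

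**5. Direction.** Under SAP 10.1 the confirmed best response is the best across all pairs of assessments. An extra scan can raise a maximum but cannot lower it, so a scan on the next therapy can add a responder and cannot remove one. EOT is the only scheduled tumour assessment after treatment ends. The realistic route is therefore confirmation of a response first seen on OP-1250, not a wholly new response. The waterfall plot in SAP 10.2 needs no confirmation, so a single such scan can set its value.

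**6. Size.** One subject is 1/50 = 2.0 points. The documents give no expected ORR. Taking two assumed rates to show the effect of removing one such case (Clopper-Pearson 95% limits):

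- 6/50 = 12% (4.5 to 24.3) becomes 5/50 = 10% (3.3 to 21.8).
- 10/50 = 20% (10.0 to 33.7) becomes 9/50 = 18% (8.6 to 31.4).

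**The case against.** The strongest reply is that the chain is long. The subject must have an unconfirmed response, stop without radiologic PD, start something new before the EOT scan, and still show CR or PR on it. The 4-week repeat scan should settle most responses on treatment, the skip rule removes many early EOT scans, and 42 days is an outer limit. Phase II ORR is a preliminary estimate with no visible test or success threshold, and 2 points is well inside ±15. All of this stands, and it limits the size of the problem.

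It does not close the gap. The repeat scan does not protect a subject who stops within 28 days of first response, and the schedule in Table 1 shows tumour scans only every second cycle from Cycle 3, with no separate 4-week confirmation visit. Nor must the EOT scan sit at the very end of its window: in the example any scan in the last 24 of the 42 days would do.

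The second reply is redaction. Parts of SAP 10 and 10.1 and of the ORR paragraph in protocol 11.3 are blacked out, and protocol 10.3.2 is partly illegible. A therapy cut-off could sit there, so a reader should not conclude that the whole plan lacks one. But the ORR derivation itself is readable, states its own exclusion, and names PD alone.

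**Conclusion.** The gap is real. Followed literally, SAP 10.1 can classify a response confirmed on another treatment as a confirmed OP-1250 response in the Phase II primary ORR, and the misclassification runs one way only. The supported size is 2 points of ORR per case at n = 50, about a seventh of the 14.5-point half-width. CBR is less exposed, because SAP 10.1 also requires at least 24 weeks on treatment.

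A reader might infer that the reported ORR will be materially inflated, or might want a count of affected subjects or a typical duration of new therapy before the scan. The documents support none of these. They give no rate of stopping without progression and no interval from last dose to next therapy. The 2-week washout in the entry criteria concerns treatment before OP-1250 and cannot stand in for that interval. The number affected is probably small. Confidence is moderate because of the redactions.

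**What to change.** Reword the exclusion in SAP 10.1 so that best and confirmed overall response both ignore any time point response dated after the earlier of:

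- first PD, and
- the start of any non-protocol anticancer therapy, meaning systemic therapy, or radiotherapy or surgery to a target lesion.

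A CR or PR not confirmed by that date counts as unconfirmed. Apply the same cut-off to the waterfall plot in SAP 10.2. Leave membership of the efficacy analysis set as it is, so that the denominator does not change.

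Name the date source. Protocol Table 1, footnote 5, records concomitant medications until the EOT visit, so the eCRF should hold the start of a new systemic therapy. The SAP 9.5 definition stops 30 days after the last dose and would miss up to 42 − 30 = 12 days of the EOT window, so it should not be used for this. Check that the eCRF also dates radiotherapy and surgery.

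The cost is one sentence and one derived date, settled before database lock. Sample size, stated precision and trial conduct are unaffected. The downside is that confirmed ORR may be slightly lower.
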